APPENDIX 1 METHODS OF CONTRACEPTION

At a minimum, subjects must agree to use one highly effective method of contraception as listed below:

HIGHLY EFFECTIVE METHODS OF CONTRACEPTION

Highly effective methods of contraception have a failure rate of < 1% when used consistently and correctly. WOCBP and female partners of male subjects, who are WOCBP, are expected to use one of the highly effective methods of contraception listed below. Male subjects must inform their female partners who are WOCBP of the contraceptive requirements of the protocol and are expected to adhere to using contraception with their partner. Contraception methods are as follows:

- 1) Progestogen only hormonal contraception associated with inhibition of ovulation.
- 2) Hormonal methods of contraception including oral contraceptive pills containing combined estrogen + progestrone, vaginal ring, injectables, implants and intrauterine devices (IUDs) such as Mirena®
- 3) Nonhormonal IUDs, such as ParaGard®
- 4) Bilateral tubal occlusion
- 5) Vasectomised partner with documented azoospermia 90 days after procedure
 - ◆ Vasectomised partner is a highly effective birth control method provided that partner is the sole sexual partner of the WOCBP trial participant and that the vasectomised partner has received medical assessment of the surgical success.
- 6) Intrauterine hormone-releasing system (IUS).
- 7) Complete abstinence
 - ◆ Complete abstinence is defined as the complete avoidance of heterosexual intercourse (refer to Glossary of Terms)
 - ◆ Complete abstinence is an acceptable form of contraception for all study drugs and must be used throughout the duration of the study treatment (plus approximately 5 half-lives of the investigational drug plus 30 days).
 - ◆ It is not necessary to use any other method of contraception when complete abstinence is elected.
 - ◆ Subjects who choose complete abstinence must continue to have pregnancy tests, as specified in [Section 5.1](#).
 - ◆ Acceptable alternate methods of highly effective contraception must be discussed in the event that the subject chooses to forego complete abstinence.
 - ◆ The reliability of sexual abstinence needs to be evaluated in relation to the duration of the clinical trial and the preferred and usual lifestyle of the subject.

UNACCEPTABLE METHODS OF CONTRACEPTION

- 1) Periodic abstinence (calendar, symptothermal, post-ovulation methods)
- 2) Withdrawal (coitus interruptus)

- 3) Spermicide only
- 4) Lactation amenorrhea method (LAM)

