g) Subjects with prior history of allogeneic transplant can participate if the transplant was performed at least 6 or more months before screening. If there is no prior history of Grade 2 + acute graft versus host disease (GVHD), no history of extensive or Grade 4 chronic GVHD, or no immunosuppressive therapy for a minimum of 4 weeks with no clinically apparent GVHD.

3. Physical and Laboratory Test Findings

Screening laboratory values must meet the following criteria (using Common Terminology Criteria for Adverse Events [CTCAE] v4.03):

- a) White blood count (WBC) $\geq 2000/\mu\text{L}$
- b) Neutrophils $\geq 1500/\mu\text{L}$
- c) Platelets $\geq 100 \times 10^3/\mu\text{L}$
- d) Hemoglobin $\geq 9.0 \text{ g/dL}$
- e) Serum creatinine $\leq 1.5 \times$ upper limit of normal (ULN) or calculated creatinine clearance $> 50 \text{ mL/min}$ (using the Cockcroft-Gault formula)

$$\text{Female CrCl} = \frac{(140 - \text{age in years}) \times \text{weight in kg} \times 0.85}{72 \times \text{serum creatinine in mg/dL}}$$

$$\text{Male CrCl} = \frac{(140 - \text{age in years}) \times \text{weight in kg} \times 1.00}{72 \times \text{serum creatinine in mg/dL}}$$

- f) Aspartate aminotransferase (AST) and alanine aminotransferase (ALT) $\leq 3.0 \times \text{ULN}$
- g) Total bilirubin (TBIL) $\leq 1.5 \times \text{ULN}$ (except subjects with Gilbert Syndrome who must have a total bilirubin level of $< 3.0 \times \text{ULN}$)

4. Age and Reproductive Status

- a) Women of childbearing potential (WOCBP) must have a negative serum or urine pregnancy test (minimum sensitivity 25 IU/L or equivalent units of human chorionic gonadotropin) within 24 hours prior to the start of study drug
- b) Women must not be pregnant or breastfeeding
- c) WOCBP must agree to follow instructions for method(s) of contraception for the duration of study treatment with nivolumab and 5 months after the last dose of study treatment {i.e., 30 days (duration of ovulatory cycle) plus the time required for the investigational drug to undergo approximately five half-lives.}
- d) Males who are sexually active with WOCBP must agree to follow instructions for method(s) of contraception for the duration of study treatment with nivolumab and 7 months after the last dose of study treatment {i.e., 90 days (duration of sperm turnover) plus the time required for the investigational drug to undergo approximately five half-lives.}

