10 GLOSSARY OF TERMS

Term	Definition
Complete Abstinence	Complete Abstinence is defined as complete avoidance of heterosexual intercourse and is an acceptable form of contraception for all study drugs. This also means that abstinence is the preferred and usual lifestyle of the patient. This does not mean periodic abstinence (eg, calendar, ovulation, symptothermal, profession of abstinence for entry into a clinical trial, post-ovulation methods) and withdrawal, which are not acceptable methods of contraception. Women must continue to have pregnancy tests. Acceptable alternate methods of highly effective contraception's must be discussed in the event that the subject chooses to forego complete abstinence.

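### Appendix 1 item 7 gives one abstinence period, with no sex label, built on the women's formula; for a man it ends 60 days before the period in criterion 4d

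*Protocol*

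**What the plan says.** Section 3.3.1 of the Protocol sets the length of contraception after the last dose separately by sex, and gives the reason each time.

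- Criterion 4c, for WOCBP: "5 months after the last dose of study treatment {i.e., 30 days (duration of ovulatory cycle) plus the time required" for about five half-lives of the drug.
- Criterion 4d opens "Males who are sexually active with WOCBP must agree to follow instructions for method(s) of contraception" and sets the period at "7 months after the last dose of study treatment {i.e., 90 days (duration of sperm turnover) plus the time required" for about five half-lives.

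The closing text of that criterion group then requires subjects, without distinction of sex, to use at least one highly effective method from Appendix 1.

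Item 7 of Appendix 1 is complete abstinence. It is the only listed method that carries its own duration. It says that abstinence "must be used throughout the duration of the study treatment (plus approximately 5 half-lives of the investigational drug plus 30 days", and adds that a subject who elects it needs no other method. It gives no separate figure for men and does not refer to 4c or 4d.

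**The concern.** Item 7 prints the 4c formula as though it applied to everyone. It was probably drafted with women in mind. It says "Subjects who choose complete abstinence must continue to have pregnancy tests", and the corresponding Glossary sentence (Section 10) reads "Women must continue to have pregnancy tests". But the label that would confine it to women is absent, and the surrounding text reaches men. The Appendix 1 lead-in says "Male subjects must inform their female partners who are WOCBP of the contraceptive requirements of the protocol" and expects men to adhere with their partners. The Glossary entry for abstinence speaks of the patient, not of women.

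Item 7 is also the only method on the list that a male subject can carry out himself. Items 1 to 4 and 6 are used by the woman, and item 5 is worded for the partner of a female participant. A man who elects abstinence is thus directed to an instruction that ends before the sperm-turnover allowance in 4d has run, and that tells him no second method is needed. What is at stake is possible conception within that allowance. Men are a substantial part of this trial: the testicular lymphoma cohort alone is planned at 20 of 65 subjects.

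**Working it through.** **Inputs**

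- Item 7, Appendix 1: 5 half-lives + 30 days.
- Criterion 4c: 5 half-lives + 30 days, stated as 5 months.
- Criterion 4d: 5 half-lives + 90 days, stated as 7 months.
- Days per month: 30.4375 (SAP Section 8).
- Half-life: not used as an outside figure. It is solved from the stated months and then shown to cancel.

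**Step 1. Do 4c and 4d agree with each other?**

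- From 4c: 5 × 30.4375 = 152.2 days; 152.2 - 30 = 122.2 days for five half-lives, or 24.4 days each.
- From 4d: 7 × 30.4375 = 213.1 days; 213.1 - 90 = 123.1 days for five half-lives, or 24.6 days each.

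The implied half-lives differ by 0.2 day. With 30-day months both criteria give exactly 120 days for five half-lives. The 5-month and 7-month figures are therefore reproduced and consistent with each other, so the discrepancy lies in item 7.

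**Step 2. Item 7 as a man would apply it**

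- With the 4c value: 122.2 + 30 = 152.2 days.
- With the 4d value: 123.1 + 30 = 153.1 days.
- Period under 4d: 213.1 days.

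**Step 3. The gap**

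- By formula: (5 half-lives + 90) - (5 half-lives + 30) = 60 days. The half-life term drops out; trial values from 15 to 30 days all return 60.
- By the rounded months: (7 - 5) × 30.4375 = 60.9 days. With 30-day months it is 60 days, and with 31-day months 62 days.

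**Step 4. Who is exposed**

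The gap matters only for a man who meets all of these conditions: he is not azoospermic (4e exempts azoospermic men); abstinence is his usual way of life, as the Glossary requires; he elects it under item 7; and he resumes intercourse with a WOCBP in the 60-day window without 4d being applied to him. The documents give no rate for this chain, so no count can be calculated.

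**The case against.** The best case against is that item 7 is a women's instruction and, as such, is exactly right. The lead-in names WOCBP and the female partners of male subjects as the users of the listed methods, most items are female methods, and the pregnancy-test line can apply only to women. Durations are set in Section 3.3.1, where men have an explicit 7-month rule, and Appendix 1 is consulted only for which methods qualify. On this view an abstinent man is outside 4d while abstinent and comes within it if he resumes intercourse with a WOCBP before 7 months, so no gap in the requirement remains. There are further safeguards. Item 7 calls for alternative methods to be discussed if abstinence is given up and for its reliability to be weighed. Investigators must counsel men who are sexually active with WOCBP. The Glossary accepts abstinence only where "This also means that abstinence is the preferred and usual lifestyle of the patient". Subjects are informed through the consent form, which is not in the file reviewed, so what men were actually told is unknown.

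Much of this stands as a limit on the consequences. It does not remove the inconsistency. The lead-in brings in female partners of male subjects and tells men to adhere, and Section 3.3.1 requires subjects of either sex to use a listed method. Criterion 4d is an entry criterion worded for men who are sexually active with WOCBP, and the counselling duty has the same scope, so an abstinent man may reasonably not see himself in either. Criterion 4e exempts azoospermic men and WOCBP who are not heterosexually active, but does not mention abstinent men. The likelihood that item 7 was written for women explains how the label came to be missing; the text still lacks it.

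**Conclusion.** The concern holds, at minor severity. As printed, item 7 applies the WOCBP period to any subject who elects abstinence, and for a man that is 60 days short of the period the Protocol itself ties to sperm turnover. The 60 days rest only on the two add-ons printed in Section 3.3.1 and need no assumption about nivolumab's half-life. The totals of about 153 and 213 days rest on the SAP's month length and on reading the stated months as exact.

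The practical reach is small. The number of men affected is unknown and may be zero, and a man who is sexually active with a WOCBP before 7 months should be managed under 4d. Eligibility, endpoints, sample size and analysis are untouched.

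**What to change.** In Appendix 1, item 7, delete the parenthesis that gives the half-life and 30-day formula. In its place, state that abstinence continues after the last dose for the period set in Section 3.3.1: criterion 4c for WOCBP (5 months) or criterion 4d for males (7 months). It would also help to limit the pregnancy-test line in item 7 to women, as the Glossary already does.

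The cost is a one-line clarification at the next protocol revision. It uses periods the sponsor has already set and changes nothing in eligibility, design, sample size or analysis.

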APPENDIX 2 KARNOFSKY PERFORMANCE SCALES

100	Normal; no complaints; no evidence of disease
90	Able to carry on normal activity; minor signs or symptoms of disease
80	Normal activity with effort, some sign or symptoms of disease
70	Cares for self; unable to carry on normal activity or do active work
60	Requires occasional assistance, but is able to care for most personal needs
50	Requires considerable assistance and frequent medical care
40	Disabled; requires special care and assistance
30	Severely disabled; hospitalization is indicated, although death not imminent
20	Very sick; hospitalization necessary; active support treatment is necessary
10	Moribund; fatal processes progressing rapidly
0	Dead

APPENDIX 3 RESPONSE CRITERIA FOR PCNSL

Subjects with PCNSL will be evaluated using the International Primary CNS Lymphoma Collaborative Group (IPCG) Criteria for PCNSL¹⁴.

Table 1: Response criteria for PCNSL				
Response	Criteria			
	Brain imaging	Corticosteroid dose	Eye examination	CSF cytology
Complete response (CR)	No contrast enhancement	None	Normal	Negative
Unconfirmed complete response (CRu)	No contrast enhancement	Any	Normal	Negative
	Minimal abnormality	Any	Minor RPE abnormality	Negative
Partial response (PR)	50% decrease in enhancing tumor	Irrelevant	Minor RPE abnormality or normal	Negative
	No contrast enhancement	Irrelevant	Decrease in vitreous cells or retinal infiltrate	Persistent or suspicious
Progressive disease (PD)	25% increase in lesion	Irrelevant	Recurrent or new ocular disease	Recurrent or positive
	Any new site of disease: CNS or systemic			

Source: Abrey et al., 2005

Complete Response (CR):

- Complete disappearance of all enhancing abnormalities on gadolinium-enhanced MRI.
- No evidence of active ocular lymphoma as defined by absence of cells in the vitreous and resolution of any previously documented retinal or optic nerve infiltrates. Chronic changes of the retinal pigment epithelium in the setting of a prior retinal or optic nerve infiltrate does not preclude the definition of a CR. Detailed ophthalmologic examination with dilated fundus examination, slit-lamp examination and color photography of the posterior pole, and lumbar puncture for cytology are required only if these studies were initially positive or became positive during treatment and if clinically indicated by new symptoms or signs.
- Lumbar puncture for CSF cytology is necessary to confirm cytologic response observed in the ventricular CSF.
- At the time a CR is determined, the patient should have discontinued corticosteroids for at least 2 weeks.
- Residual lesions (other than lesions < 10 mm) if presumed to be non-malignant should be further investigated (eg, by PET scans) before CR can be accepted.
- If there was evidence of PET abnormality suspicious for systemic disease then PET has to be repeated to confirm CR (Radiology comment)

- All subjects who appear to achieve CR require the following:
 - Confirmation scan at 8 weeks
 - Repeat CSF cytology, bone marrow biopsy and aspirate, and ophthalmologic examination if involved at baseline

Unconfirmed CR (CRu): Any patient who fulfills all criteria for CR but continues to require corticosteroid therapy at any dose should be considered an unconfirmed CR. Subjects with a persistent minor abnormality on follow-up ophthalmologic examination (persistent non- malignant cells in the vitreous, alteration of the retina/optic nerve that is not consistent with tumor infiltration) may be considered a CRu if this abnormality is unlikely to represent ocular lymphoma.

Partial response (PR) requires all of the following:

- A $\geq 50\%$ decrease in the contrast-enhancing lesion seen on MRI as compared with baseline imaging.
- Corticosteroid dose is irrelevant to the determination of PR.
- Ophthalmologic examination should show a decrease in the vitreous cell count or retinal/optic nerve cellular infiltrate but may continue to show persistent malignant or suspicious cells. Color photos of the posterior pole of the eye should be obtained to document improvement in retinal/optic nerve infiltrates.
- CSF cytologic examination may be negative or continue to show persistent malignant or suspicious cells in subjects with a $\geq 50\%$ decrease in the primary brain lesion.
- No new sites of disease. In the setting of primary leptomeningeal lymphoma, PR is not recognized; all subjects should be categorized as CR, CRu, stable disease, or progressive disease.

Stable disease (SD) is defined as less than a PR but is not progressive disease (PD).

Progressive disease requires the following:

- A more than 25% increase in the contrast-enhancing lesion seen on MRI as compared with baseline or best response (comparison should be made to the smallest of multiple lesions).
- Progression of ocular disease as indicated by an increase in the vitreous cell count or progressive retinal or optic nerve infiltration.
- Appearance of any new lesion or site of disease (ocular, leptomeningeal or systemic) during or at the end of therapy.

Relapsed disease (only applicable to subjects with a prior CR, CRu) requires the following:

- Appearance of any new lesion.

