Subjects who are unable (due to existent medical condition, ie, pacemaker or implantable cardioverter-defibrillator device) or unwilling to have a brain MRI at baseline are excluded from the study ([Section 3.3.4](#)). Subjects who become unable to undergo MRI imaging after enrollment may continue in the study for assessment of OS as long as there is no safety issue which would require monitoring by MRI.

Study sites will retain local access to the imaging results for safety and efficacy reading purposes. The study investigator will review the local MRI results as clinically appropriate to ensure that any potentially emergent clinical situations are addressed in a timely fashion. Clinically significant radiologic findings or changes from baseline scans will be coded as AEs or SAEs according to the criteria described below in [Section 6](#).

At baseline, for staging purposes all PCNSL subjects will undergo the following procedures:

- Gadolinium-enhanced MRI of the brain
- Gadolinium-enhanced MRI of the spine (for subjects with spinal symptoms)
- Whole-body FDG-PET or CT scan of the neck, chest, abdomen, pelvis, and other relevant body parts with suspected or known disease (to exclude patients with systemic disease)
- Lumbar puncture for CSF cytology (before/1 week after surgical biopsy, when applicable)
- Detailed ophthalmological examination, with dilated fundus examination, slit-lamp examination, and color photography of the posterior pole
- Bone marrow biopsy with aspirate, only if clinically indicated.

If MRI of the spine, ophthalmological examination, CSF cytology, or bone marrow biopsy are positive for lymphoma involvement at baseline, these tests must be repeated for confirmation of objective response.

PTL

All PTL subjects will undergo fluorodeoxyglucose (FDG) PET-CT scans at the timepoints specified in [Table 5.1-3](#) for baseline assessment and on study response assessment purposes. Investigators may obtain more frequent follow-up FDG PET-CT scans as medically indicated. Local radiologic assessment of tumor measurements will be used for clinical management and investigator-assessed clinical endpoints.

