Study sites will retain local access to the imaging results for safety and efficacy reading purposes. The study investigator will review the local FDG PET-CT results as clinically appropriate to ensure that any potentially emergent clinical situations are addressed in a timely fashion. Clinically significant radiologic findings or changes from baseline scans will be coded as AEs or SAEs according to the criteria described below in [Section 6](#).

At baseline, for staging purposes all PTL subjects will undergo the following procedures:

- FDG PET/CT scan
- Gadolinium-enhanced MRI of the brain
- Gadolinium-enhanced MRI of the spine (in subjects with spinal symptoms)
- Bone marrow biopsy with aspirate, if clinically indicated
- Lumbar puncture for CSF cytology, if clinically indicated
- Eye examination for PTL patients with CNS involvement

If brain and/or spine MRI, bone marrow biopsy, or CSF cytology are positive for lymphoma involvement at baseline, these tests must be repeated for confirmation of objective response.

On-study Assessment of Response

PCNSL

Assessment of treatment response in subjects with PCNSL while on study requires the following assessments:

- Gadolinium-enhanced MRI scan of the brain
- Gadolinium-enhanced MRI scan of the spine, if positive at baseline or if clinically indicated
- Detailed ophthalmological examination with dilated fundus examination, slit-lamp examination, and color photography of the posterior pole, if clinically indicated and for confirmation of objective response
- Whole-body CT scan, if clinically indicated
- Lumbar puncture for CSF cytology, if clinically indicated
- Bone marrow biopsy with aspirate, if clinically indicated

The criteria for response assessment are illustrated in [Appendix 3](#). Additionally, objective response requires confirmation by repeat brain MRI at 8 weeks from the initially documented response. If MRI of the spine, ophthalmological examination, CSF cytology, or bone marrow biopsy are positive for lymphoma involvement at baseline or on-study when warranted by symptoms, these tests should be also repeated at 8 weeks for confirmation of objective response.

PTL

Assessment of treatment response in subjects with PTL while on study requires the following assessments:

- FDG PET-CT scan
- Bone marrow biopsy with aspirate, if clinically indicated
- Gadolinium-enhanced MRI scan of the brain and/or of the spine, if clinically indicated
- Lumbar puncture for CSF cytology, if clinically indicated

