Any disease not selected as measured, dominant disease and truly assessable disease should be considered not measured. These sites include any nodes, nodal masses, and extranodal sites not selected as dominant or measurable or that do not meet the requirements for measurability but are still considered abnormal, as well as truly assessable disease, which is any site of suspected disease that would be difficult to follow quantitatively with measurement, including pleural effusions, ascites, bone lesions, leptomeningeal disease, abdominal masses, and other lesions that cannot be confirmed and followed by imaging. In Waldeyer's ring or in extranodal sites (eg, GI tract, liver, bone marrow), FDG uptake may be greater than in the mediastinum with complete metabolic response, but should be no higher than surrounding normal physiologic uptake (eg, with marrow activation as a result of chemotherapy or myeloid growth factors).

All other lesions (or sites of disease) including non-measurable lymph nodes should be identified as non-target lesions and should also be recorded at baseline. Measurements are not required and these lesions should be followed as 'present', 'absent', or in rare cases 'unequivocal progression'. In addition, it is possible to record multiple non-target lesions involving the same organ as a single item on the CRF (eg, 'multiple enlarged pelvic lymph nodes' or multiple liver nodules').

Bone Marrow Assessments

Bone marrow assessments should be done only if clinically indicated in both subjects with PCNSL or PTL. The biopsy/aspirate performed within 90 days prior to obtaining informed consent must be documented at screening or a bone marrow biopsy/aspirate must be performed during the screening period if clinically indicated. For PCNSL or PTL subjects with bone marrow involvement at screening, a bone marrow biopsy and aspirate will be required to confirm an objective response.

In addition to efficacy assessments, additional, optional, bone marrow biopsy and aspirate samples may be collected and submitted for biomarker studies.

CSF Assessments

CSF cytology should be done if clinically indicated. If performed within 90 days prior to obtaining informed consent they must be documented at screening or a lumbar puncture must be performed during the screening period. For PCNSL or PTL subjects with CSF involvement at screening, a lumbar puncture with CSF collection will be required to confirm an objective response.

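### The CR rule in Appendix 3 can be read as waiving repeat eye and CSF tests in baseline-positive subjects without new symptoms, contrary to its own last bullet and Section 5.4.1

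*Protocol*

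**What the plan says.** Two places in the Protocol set a narrow condition for repeat testing in PCNSL.

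- Appendix 3, second CR bullet, on when the detailed eye examination and the CSF sample have to be obtained: "required only if these studies were initially positive or became positive during treatment and if clinically indicated by new symptoms or signs".
- Section 5.4.1, On-study Assessment of Response, PCNSL list: lumbar puncture is to be done when clinically indicated. The eye item in the same list also names confirmation of response as a reason; the lumbar puncture item does not.

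Other places set a broader condition.

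- Appendix 3, last CR bullet: "All subjects who appear to achieve CR require the following", followed by a confirmation scan and "Repeat CSF cytology, bone marrow biopsy and aspirate, and ophthalmologic examination if involved at baseline". There is no symptom condition.
- Section 5.4.1, Baseline Staging, PCNSL: if spine MRI, eye examination, CSF cytology or marrow "are positive for lymphoma involvement at baseline, these tests must be repeated for confirmation of objective response".
- Section 5.4.1, On-study Assessment, paragraph after the PCNSL list: for tests positive at baseline, or on study when symptoms warranted them, "these tests should be also repeated at 8 weeks for confirmation of objective response".
- Section 5.4.1, CSF Assessments: "For PCNSL or PTL subjects with CSF involvement at screening, a lumbar puncture with CSF collection will be required to confirm an objective response".
- Appendix 3, Table 1: CR needs a normal eye examination and negative CSF cytology. The second CR bullet itself defines ocular clearance as "absence of cells in the vitreous and resolution of any previously documented retinal or optic nerve infiltrates".

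BOR, in Protocol Section 8.3.1 and SAP Section 4.1, is the best designation recorded before progression or subsequent therapy. That definition mentions neither confirmation nor a compartment that was not re-tested.

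**The concern.** One response category carries two instructions about which tests must precede it. They differ for an identifiable group: subjects with CSF or ocular disease at baseline, a cleared brain MRI and no new symptoms. Such subjects can be enrolled, since Section 3.3.2 excludes intraocular disease only when there is no evidence of brain disease. The SAP expects them: Section 7.3.2 tabulates ocular involvement and Section 7.5.1 plans a listing of slit-lamp results. Appendix 4 also applies the Appendix 3 criteria to CNS lesions in PTL.

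A test not done at the time of apparent response cannot be recovered at analysis. Under Table 1, no enhancement with persistent or suspicious CSF is a row of PR, not CR. What is at stake is therefore the split between CR and lesser categories, which SAP Section 7.5.1 reports as BOR by category, and the duration-of-CR analysis announced in the Protocol synopsis.

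**Working it through.** The question is textual, so the rules are set side by side. The bullet-2 sentence is read in two ways: both conditions needed (prior positivity and new symptoms), or symptoms as a further trigger (either is enough).

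| Subject | Bullet 2, both needed | Bullet 2, either enough | Last CR bullet | Section 5.4.1 confirmation rules |
|---|---|---|---|---|
| Positive at baseline, no new symptoms | not required | required | required | required |
| Positive at baseline, new symptoms | required | required | required | required |
| Positive only on study, no new symptoms | not required | required | silent | not clearly required |
| Positive only on study, new symptoms | required | required | silent | required |

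**Row 1 is the conflict.** With both conditions needed, bullet 2 gives the opposite answer to the last bullet of its own list and to Section 5.4.1. With either enough, the conflict disappears. The lumbar puncture item in the on-study list adds to the difficulty, because without a clinical indication it does not call for the test in row 1.

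**Rows 3 and 4** matter less for CR. A new site of disease on study is already progression under Appendix 3.

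**Effect on the CR rate.** The planned PCNSL cohort is 45 treated subjects, and each reclassified subject shifts the rate by 1/45 = 0.022, or 2.2 percentage points. The total shift would be

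(subjects positive at baseline) × P(MRI clears) × P(test skipped) × P(disease persists) / 45.

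The documents give none of the four inputs, so no total is offered.

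**Effect on ORR.** SAP Section 4.1 counts CR, CRu and PR alike, and the PR text in Appendix 3 tolerates persistent CSF cells when the brain lesion has shrunk by at least half. Moving a subject from CR to PR leaves the numerator unchanged. There are three exceptions:

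- an untested compartment that had in fact progressed (PD);
- primary leptomeningeal lymphoma, where Appendix 3 does not recognise PR;
- an involved eye not re-examined, because PR also expects the eye examination to show a decrease.

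To scale these exceptions, the plan's benchmark of 13/45 = 28.9% gives an exact Clopper-Pearson 95% interval of 16.4% to 44.3%, which reproduces the plan's table. Losing one responder gives 12/45 = 26.7% (14.6% to 41.9%), still above the 14% reference. Losing two gives 11/45 = 24.4% (12.9% to 39.5%), which no longer excludes it. This shows sensitivity at the benchmark; it is not a forecast.

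**The case against.** The strongest reply is that the plan, read as a whole, already settles the matter. The last CR bullet covers every apparent CR. Section 5.4.1 requires the repeat in several places. Table 1 needs a normal eye and negative CSF, and known ocular disease cannot be shown to have cleared without an examination. The *and if* in bullet 2 can also be additive: the eye item in the on-study list uses *and* to add a reason for testing, and the same reading of bullet 2 agrees with everything else. In addition, the CR rate is not a listed primary or secondary endpoint. Duration of CR appears in the synopsis but not in Protocol Section 8.4.2.1 or SAP Section 7.5.1. The Imaging Review Charter is not among the documents, and the efficacy rows of Table 5.1-2 cannot be read in the public text; either may resolve the point.

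Much of this stands. A reader might infer that the plan permits CR with known CSF or ocular disease untested. The documents do not support that: it happens only if a site follows bullet 2 or the on-study list in preference to the broader text. A reader might also infer that ORR is inflated, or multiply an assumed prevalence into a total number of wrong CRs. Neither follows, because ORR pools the response categories and such a product leaves out the chances that the test is skipped and that disease persists.

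What the reply does not remove is that a response criterion supports opposite instructions for the same subject. The narrower reading has a second foothold in the lumbar puncture item, and the BOR definition contains no safeguard.

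**Conclusion.** The inconsistency is real and should be corrected. Bullet 2 can be read to waive repeat testing in baseline-positive subjects without new symptoms, and the on-study lumbar puncture item leans the same way. The last CR bullet, the other parts of Section 5.4.1 and Table 1 require the result. If the narrower text were followed, a CR could be recorded where the criteria may support only a lesser category.

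The size is 2.2 points on the PCNSL CR rate per subject affected, assuming the planned 45 treated subjects. How many would be affected is unknown. Any duration-of-CR summary would be affected too. ORR is largely unaffected, with the three exceptions shown in the working. The conclusion rests on the public Protocol and SAP; a charter rule requiring the re-test would reduce the risk at BICR but would not remove the contradiction in the Protocol.

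**What to change.** 1. In Appendix 3, reword the second CR bullet so that confirming CR calls for the repeat eye examination or CSF cytology whenever that compartment was involved at baseline, with new symptoms or signs as an additional trigger. State separately what applies to a compartment that became positive only on study.
2. In Section 5.4.1, bring the on-study lumbar puncture item into line by adding confirmation of response in subjects with baseline CSF involvement, as the eye item already does.
3. In the BICR charter and the SAP definition of BOR, state that CR is not assigned while a baseline-positive CSF or eye compartment has not been re-tested, and that the subject is then classified by the remaining Appendix 3 criteria. Do not make PR automatic: PR also expects a documented decrease on eye examination, so the rule must say explicitly how an unexamined involved eye is handled. That choice can reach ORR.

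The cost is two wording changes and one derivation rule. No procedure is added for baseline-positive subjects, because the last CR bullet and Section 5.4.1 already require the tests. For subjects positive only on study and without symptoms, the sponsor should check whether the chosen wording goes beyond Section 5.4.1.
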